#### **Accountability criteria**

The sponsor will classify the adverse event, based in their causation relation with the investigational product, following the Karch y Lasagna (1977) algorithm, as:

- Final: there is reasonable temporal sequence between the drug administration and the existence of the adverse event. This event matches with the adverse reaction described for the investigational product, improves with the omission and reappears after its re-administration and can't be explained by other causes.
- Probable: there is reasonable temporal sequence between the investigational product administration and the appearance of the adverse event. This event matches with the adverse reaction described for the drug, improves with the omission and can't be explained by other causes.
- Possible: there is reasonable temporal sequence between the investigational product administration and the appearance of the adverse event. This event matches with the adverse reaction described for the drug but can be explained by other causes.
- Conditional or improbable: there is reasonable temporal sequence between the investigational product administration and the appearance of the adverse event. This event does not matches with the adverse reaction described for the drug and can be explained by other causes.
- Not related: there is no reasonable temporal sequence between the investigational product administration and the appearance of the adverse event. This event does not matches with the adverse reaction described for the drug and can be explained by other causes.

For expedited reporting purposes it is considered as related the categories: final, probable and possible from Karch y Lasagna (1977) algorithm and as not related the category conditional or

	
improbable of that algorithm.
 
The determination of the possible relation with the study treatment is responsibility of the principal investigator of the site or the person designated by him.


Serious Adverse Event (SAE) and Serious Adverse Reaction (SAR)
	
Any adverse event or adverse reaction that, at any dose:
 
 
○ is fatal (results in death),
 
○ initial or prolonged inpatient hospitalization,
 
○ a life-threatening experience (that is, immediate risk of dying, defined as an event in which the patient was at risk of death at the time of the event; it does not refer to an event which hypothetically might have caused death if it were more severe),
 
○ persistent or significant disability/incapacity,
 
○ congenital anomaly/birth defect or
 
○ an important medical event, defined as a medical event that may not be immediately life-threatening or result in death or hospitalization but, based on appropriate medical and scientific judgment, may jeopardize the patient or may require intervention (eg. medical, surgical) to prevent one of the other serious outcomes listed above.
 
 
Do not confuse the concept “serious”, described before, with “severe” which refers to the intensity of the AE or AR (minor/mild/severe).
 
Any temporary increase in the severity of a symptom or previous sickness that happens after the baseline of the study is considered also as an adverse event.

Suspected Unexpected Serious Adverse Reaction (SUSAR)
	
Any serious adverse reaction whose nature, intensity or consequences do not correspond with the reference information for the investigational product (Summary of Product Characteristics [SmPC]).
 
The unexpected nature of an adverse reaction is based in the fact of not being observed previously and not in what could be advanced based on the pharmacological properties of the drug.

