### **5.8.1 Process for urgent unblinding**

In general, unblinding of participants during the conduct of the clinical trial is not allowed unless there are compelling medical or safety reasons to do so.

Any serious adverse event considered by the investigator to be related to the blinded treatment medication (0.005% estriol vaginal gel/placebo vaginal gel) should be reported as such to the sponsor via the appropriate SAE reporting form.

There will be two complete sets of randomization codes. One will be kept by the GEICAM Pharmacovigilance department and the other will be distributed among the investigators. The emergency codes should be kept in a safe but accessible place in the event they should be opened. Each investigator will receive the necessary envelopes closed to randomize a determined number of patients. Each envelope will contain the details of the treatment that the patient is receiving. In the case of emergency the envelope must be opened to determine the treatment being administered.

The randomization envelopes can only be opened in an emergency. When the investigator opens the envelope he/she must record the date, the time and the reason he/she has had to do so and will keep this information with the eCRF documentation. He/she should also immediately inform the study monitor that a treatment code has been opened. As per regulatory reporting requirement, it will unblind the identity of the study medication for all unexpected SAES that are considered by the investigator to be related to the study drug. Details of subjects who are unblinded during the study will be included in the Clinical Study Report.

---

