### 6.3.3 Management, Timing and Assessment of Adverse Events

AE Classification
	
Adverse events should be classified following MedDRA. The investigators team must have access to MedDRA.
 
The causal relation between the investigational product and the AE will be assessed by the investigator using the Karch y Lasagna (1977) algorithm.
 
Note that, for the purpose of this protocol, the following circumstances – with or without associated adverse event/reaction - should be included the data base and will be submitted to the sponsor - that is, managed in the same way and time as adverse events/reactions:
 
 
• Overdose, abuse, misuse
 
• Off-label use
 
• Medication error
 

Procedure to notify an AE to Sponsor
	
The site will enter the following events in the eCRF:
 
 
○ All adverse events that occur after enrollment.
 
○ Preexisting conditions that get worse during the study.
 
○ The evaluation of the possible relationship of each adverse event to the study drug or protocol procedure.
 
○ The circumstances and data that causes the suspension of the treatment of a patient due to an adverse event.
 
○ The events leading to the clinical outcome of death from disease progression will be included in the efficacy analysis unless and are not recorded as adverse events, unless the investigator believes they could have been caused by the study drug.
 
 
Data Management of GEICAM will notify all these events to the sponsor as agreed between the parties.

Timing and assessment of AE (see Protocol Attachment 3)
	
The site staff will report on the eCRF the information of the AE in the following periods:
 
 
• Baseline (after ICD and before study treatment): study site personnel will note the occurrence and nature of each patient's medical condition(s) and preexisting conditions in the appropriate section of the eCRF. If a patient never receives study treatment but experiences an adverse event after the ICD is signed, ONLY events
 

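### Every causality category counted as related requires a match with an already described reaction, so a serious reaction of a new nature cannot be classed as related

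*Protocol*

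**What the plan says.** Protocol section 6.3.2, Table 2 (Accountability criteria), defines five categories. Three of them carry the same condition:

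- Final: "This event matches with the adverse reaction described for the investigational product, improves with the omission and reappears after its re-administration", with no other explanation.
- Probable: "This event matches with the adverse reaction described for the drug, improves with the omission and can't be explained by other causes".
- Possible: "This event matches with the adverse reaction described for the drug but can be explained by other causes".

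Conditional or improbable keeps the plausible timing but reverses the match: "This event does not matches with the adverse reaction described for the drug and can be explained by other causes". Not related differs from it only in lacking plausible timing.

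The mapping follows: "For expedited reporting purposes it is considered as related the categories: final, probable and possible". Conditional or improbable is mapped to not related.

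The same table makes relatedness part of being an adverse reaction. It defines a SUSAR as a serious adverse reaction whose "nature, intensity or consequences do not correspond with the reference information for the investigational product", and it bases unexpectedness on the reaction not having been observed before.

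On the code-break, section 5.8.1 says "it will unblind the identity of the study medication for all unexpected SAES that are considered by the investigator" as drug-related. Section 6.3.5 sets a 15-day limit for SUSARs, or 7 days if fatal or life-threatening.

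On the assessor, the Accountability criteria open with the sponsor classifying the event and close by giving the determination to the site's principal investigator or a designee. Section 6.3.3 says causality "will be assessed by the investigator using the Karch y Lasagna (1977) algorithm".

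**The concern.** Relatedness and expectedness are separate questions. Relatedness asks whether the drug may have caused the event; expectedness asks whether the reference information already covers it. Table 2 builds a form of expectedness into relatedness. If a match with a described reaction is needed before an event can be related, an event that is new in nature cannot be both related and unexpected. Yet that is the combination for which SUSAR reporting and the code-break in section 5.8.1 exist.

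The stakes are higher than usual because this is a safety trial in women on aromatase inhibitors. Section 1.5 acknowledges that the supporting data came from healthy postmenopausal women. A reaction not described before is one of the things the trial should be able to recognise.

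**Working it through.** There is no sample size, power or alpha figure to reproduce. The check is to apply the five definitions as written to every combination of the five yes/no criteria they use: plausible timing, match with a described reaction, improvement on withdrawal, reappearance on re-exposure, and another possible cause. That gives 2^5 = 32 combinations.

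| Timing | Match | Other cause | Combinations | Category | Counted as |
|---|---|---|---|---|---|
| yes | yes | yes | 4 | Possible | related |
| yes | yes | no; improves on withdrawal | 2 | Probable (one also Final) | related |
| yes | yes | no; does not improve | 2 | none | – |
| yes | no | yes | 4 | Conditional or improbable | not related |
| yes | no | no | 4 | none | – |
| no | no | yes | 4 | Not related | not related |
| no | no | no | 4 | none | – |
| no | yes | yes or no | 8 | none | – |

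The rows sum to 4 + 2 + 2 + 4 + 4 + 4 + 4 + 8 = 32.

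1. **Related outcomes.** 4 + 2 = 6 combinations reach a related category, and all 6 have the match. Of the 4 + 4 + 4 + 4 = 16 combinations without a match, 0 do.
2. **Plausibly timed, no match.** These are 8 combinations. Four are declared not related and four have no category. The four without a category are those with no other explanation, and they include the case that improves on withdrawal and returns on re-exposure.
3. **Plausibly timed, match, no other cause, no improvement.** These 2 combinations have no category. A fatal event of a described type would fall here. If another cause were present, the same event would be possible, hence related. Removing the competing explanation takes it out of the related group.
4. **Set against the other sections.** A SUSAR must be an adverse reaction, hence related, and must depart from the reference information. For an event new in nature, step 1 rules out related. Sections 5.8.1 and 6.3.5 nevertheless assume such events can be identified, unblinded and reported. The texts cannot all be followed.
5. **Is there an override?** Section 6.3.3 ties the investigator to this same algorithm. Section 6.3.4 lets the sponsor suspect a SUSAR but gives no criterion outside Table 2. No override is written.

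**The case against.** The case on the other side is substantial, and much of it limits the point. A reader might infer four stronger things that the protocol does not support.

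- **That no SUSAR could ever arise.** The definition covers nature, intensity or consequences. A described reaction of unexpected intensity or consequence can match, be possible and become a SUSAR. Only reactions new in nature are blocked.
- **That serious events would be lost.** Section 6.3.4 sends SAEs to the study group's pharmacovigilance department and the sponsor within 24 hours, regardless of relatedness, up to 30 days after the last dose. After that, section 6.3.3 and Attachment 3 collect only SAEs thought related to treatment or procedures, so there the classification does control collection.
- **That new reactions escape all expedited reporting.** Section 6.3.5 has a separate 15-day route for information that could alter the benefit/risk balance, and it does not use the Table 2 categories.
- **That the safety endpoint is biased.** The endpoint in section 2.4 is adverse events by MedDRA, with no relatedness condition. Section 8.2.8 summarises them regardless of causality as well as by relationship, and its between-arm test is on adverse events as such. The primary endpoint is serum FSH.

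Two further objections concern the check itself. Collapsed to timing, match and other cause, four of the eight cells have no category at all, but three of those lack plausible timing, so only one is a relevant gap. That is correct. Also, Table 2 does not say where a reaction must be described. If the general literature on estriol counts, a reaction absent from the SmPC could match and still be unexpected. This softens the conflict without removing it, because a reaction never observed before cannot match a description anywhere.

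Experienced assessors may well use judgement, but they would be departing from the text.

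**Conclusion.** The concern stands as an internal contradiction and an incomplete classification. As written, 0 of 16 non-matching combinations can be related. A plausibly timed serious event of an undescribed nature is either declared not related or left unclassified, and so is a matching event with no other cause that does not improve on withdrawal left unclassified. The 0 of 16 is a property of the definitions, not an estimate of how many events would be misclassified.

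The reach is limited to SUSAR status, the code-break for unexpected related SAEs, the related-AE summaries, and SAE collection more than 30 days after the last dose.

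The conclusion rests on a literal reading of Table 2 and on section 6.3.3 binding the investigator to it. Whether Table 2 reproduces the cited algorithm faithfully cannot be checked from the protocol and is not relied on; a faithful copy would conflict with the other sections just the same.

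**What to change.** - Remove the match with a described reaction as a necessary condition of final, probable and possible alike. Removing it from possible alone would leave an undescribed event with positive withdrawal and re-exposure evidence unable to rise above possible.
- Judge expectedness as a separate step, against the SmPC.
- Use one test of relatedness and make the categories exhaustive. A plausibly timed event with no other cause should always be classed as related, with response to withdrawal and re-exposure only grading the strength. Where another cause exists, say what separates possible from conditional or improbable once the match no longer does.
- Name one assessor. The opening of the Accountability criteria (sponsor) must be reconciled with their close and with sections 5.8.1, 6.3.3 and 8.2.8 (investigator).

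The cost is wording in Table 2 and the SAE form. The downside is small: a few more events will be handled as suspected reactions.

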### 6.3.3 Management, Timing and Assessment of Adverse Events

AE Classification
	
Adverse events should be classified following MedDRA. The investigators team must have access to MedDRA.
 
The causal relation between the investigational product and the AE will be assessed by the investigator using the Karch y Lasagna (1977) algorithm.
 
Note that, for the purpose of this protocol, the following circumstances – with or without associated adverse event/reaction - should be included the data base and will be submitted to the sponsor - that is, managed in the same way and time as adverse events/reactions:
 
 
• Overdose, abuse, misuse
 
• Off-label use
 
• Medication error
 

Procedure to notify an AE to Sponsor
	
The site will enter the following events in the eCRF:
 
 
○ All adverse events that occur after enrollment.
 
○ Preexisting conditions that get worse during the study.
 
○ The evaluation of the possible relationship of each adverse event to the study drug or protocol procedure.
 
○ The circumstances and data that causes the suspension of the treatment of a patient due to an adverse event.
 
○ The events leading to the clinical outcome of death from disease progression will be included in the efficacy analysis unless and are not recorded as adverse events, unless the investigator believes they could have been caused by the study drug.
 
 
Data Management of GEICAM will notify all these events to the sponsor as agreed between the parties.

Timing and assessment of AE (see Protocol Attachment 3)
	
The site staff will report on the eCRF the information of the AE in the following periods:
 
 
• Baseline (after ICD and before study treatment): study site personnel will note the occurrence and nature of each patient's medical condition(s) and preexisting conditions in the appropriate section of the eCRF. If a patient never receives study treatment but experiences an adverse event after the ICD is signed, ONLY events
 

	
the investigator believes may have been caused by a protocol procedure will be reported to GEICAM via eCRF.
 
 
• During treatment with the study treatment: during the study, site personnel will record any change in the condition(s) and the occurrence and nature of any adverse events. A CTCAE grade rating will be assigned before each cycle for any adverse event experienced during the previous cycle.
 
• 30-day post-discontinuation follow-up period: each patient will have a 30-day post-discontinuation follow-up evaluation approximately 30 days following the discontinuation of study treatment. Patients should be closely followed for study treatment adverse events in order to detect delayed toxicity. If drug-related toxicity is present beyond 30 days post-discontinuation, patients must be followed until the toxicity resolves or improved to baseline, the relationship is reassessed as unrelated, the investigator confirms that no further improvement can be expected, another therapy is initiated, or death.
 
• Long-Term Follow-up Period (after the 30-day post-discontinuation): only new and ongoing SAEs thought to be related to study treatment or protocol procedures should be documented on the eCRF and immediately reported to GEICAM via the designated transmission method, even if the study has been closed.
 

--	---

#### 6.3.4 Management, Timing and Assessment of SAEs

Timing of SAEs (see Protocol Attachment 3)
	
All the SAEs (either spontaneously or during the trial visits) will be collected since the patient signs the Informed Consent Document (ICD).
 
All the SAEs must be documented in the medical record of the patient and in the eCRF. A follow up of all the SAEs should be done until they are solved or until the toxicity is considered irreversible.

SAEs which do not need to be notified to the Pharmacovigilance Department of the Sponsor
	
The following events are not considered SAEs:
 
 
○ A visit to the emergency room or other hospital department lasting less than 24 hours that does not result in admission (unless considered an “important
 

	
medical event” or a life-threatening event).
 
 
○ Elective surgery planned before signing consent.
 
○ Hospitalization which is due solely to a planned study visit and without prolongation.
 
○ Routine health assessment requiring admission for baseline/trending of health status (eg. routine colonoscopy).
 
○ Medical/surgical admission for purpose other than remedying ill health state that was planned before study entry. Appropriate documentation is required in these cases.
 
○ Admission encountered for another life circumstance that carries no bearing on health status and requires no medical/surgical intervention (eg. lack of housing, economic inadequacy, caregiver respite, family circumstances, administrative).
 
○ Progression of the malignancy during study (including signs and symptoms of progression), unless the outcome is fatal and death occurred before end of treatment. Thereafter death due to disease progression has not to be reported as SAE.
 
○ Hospitalization due to signs and symptoms of disease progression.
 
○ An overnight stay in the hospital that is only due to transportation, organization or accommodation problems and without medical background.
 
 
They will be reported in the eCRF and in the patient record.
 
The rest of SAEs must be notified as described as follows.


Procedure to notify a SAE to the Pharmacovigilance Department of GEICAM and Sponsor
	
The SAEs must be notified to the Pharmacovigilance Department of GEICAM and to the Sponsor at the same time. A member of the investigator team must complete and sign the SAE notification form which will be sent by fax/mail, immediately and always during the 24 hours following knowledge of the SAE:

	
Pharmacovigilance Department of GEICAM
 
[contact]
 
[contact]
 
ITF RESEARCH PHARMA S.L.U
 
[contact]
 
Email: [contact]
 
Once received, GEICAM and the Sponsor will contact each other to make sure that both parties have received the SAE.
 
The SAE will be reviewed by the Pharmacovigilance Department of the Sponsor and, if necessary, will ask more information to the investigator.
 
When additional information is obtained about the SAEs, or this is solved or is improbable it will change, a follow-up report must be also completed and sent by fax/mail, immediately and always during the following the 24 hours to the Pharmacovigilance Department of Sponsor.
 
If the Sponsor suspects that the SAE could be a SUSAR, the investigator should give the follow up information requested.
 
All SAEs from the time the patient have the first dose of the study drug through 30 days following the last administration of study drug must be reported according to the procedure described below. All SAE regardless of timing must be reported, if considered related to study drug.
 
Likewise, progression of a patient's underlying condition leading to one of the above should also not be reported as a SAE, but documented as primary study endpoint.
 
All SAEs will be followed-up by the investigator until satisfactory resolution. Annually all SARs will be reported as the DSUR to the competent authorities and the leading ethics committee, including all SUSARs.
 
Withdrawal from further treatment shall be at the discretion of the investigator.

Death on Study	
Any death occurring during the active treatment part of the study and within 30 days following the last treatment must be reported to GEICAM and to the sponsor within 24 hours, regardless of the relation to study drug(s), and has to be

	
reported on the death report form section of the eCRF.
 
The cause of death should be documented (cancer-related, treatment-related, cancer- and treatment-unrelated). Autopsy reports should be collected whenever possible and sent to GEICAM.
 
Deaths that occur due to tumor progression do not have to be reported as a SAE unless they occurred before end of treatment.
 
Deaths after the end of study which are considered to be related to study treatment have to be reported as SAEs.
 
To the extent feasible sufficient information including relevant laboratory values, ECG, scan, biopsy or autopsy results must be provided by the investigator in the SAE narrative (even if investigator determines the SAE is not related) so as to permit an independent causality assessment by a Competent Authority.

--	---

